There is no defined clinical hypothesis for this study. This study is designed to demonstrate that the updated DEX PS DDS Applicator (that incorporates the final, to be-marketed design) delivers the DEX PS DDS Implant to the vitreous cavity and is suitable for commercial use in patients with macular edema due to retinal diseases. No changes are being made to the DEX PS DDS Implant. As the safety of the DEX PS DDS Implant is already well characterized and is the same as the currently marketed product, the duration of the proposed study is designed to capture investigator experience and any complaints associated with the DEX PS DDS Implant administration using the updated DEX PS DDS Applicator. The planned assessments include best-corrected visual acuity (BCVA), biomicroscopic slit lamp examination, ophthalmoscopy, and intraocular pressure (IOP). Adverse events (AEs) will also be collected. The treatment administration assessment form will be collected to evaluate investigator experience with and performance of the updated DEX PS DDS Applicator and the currently-approved DEX-PS DDS Applicator as a comparator. These parameters are sufficient to determine whether the updated DEX PS DDS Applicator delivers the DEX PS DDS Implant to the vitreous cavity.

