6 SAFETY CONSIDERATIONS

6.1 Complaints and Adverse Events

Complaints

A complaint is any written, electronic, or oral communication that alleges deficiencies related to the physical characteristics, identity, quality, purity, potency, durability, reliability, safety, effectiveness, or performance of a product/device. Complaints associated with any component of this investigational product must be reported to AbbVie.

Product Complaint

A product complaint is any complaint related to the biologic or drug component of the product or to the medical device component(s).

For a product this may include, but is not limited to, damaged/broken product or packaging, product appearance whose color/markings do not match the labeling, labeling discrepancies/inadequacies in the labeling/instructions (e.g., printing illegible), missing components/product, device damage or not working properly, or packaging issues.

Product complaints concerning the investigational product and/or device must be reported to AbbVie within 24 hours of the study site's knowledge of the event.

Reporting will be done via electronic data capture (EDC). The date the product complaint details are entered into EDC and the form is saved represents the date reported to AbbVie. A back-up paper form

will be provided for reporting complaints related to unassigned product or in the event of an EDC system issue. If a back-up paper form is used, the date the form is emailed to [contact] represents the date reported to AbbVie.

All follow-up information is to be reported to the sponsor (or an authorized representative) and documented in source as required by the sponsor. Product complaints associated with adverse events will be reported in the study summary. All other complaints will be monitored on an ongoing basis. Product complaints occurring during the study will be followed up to a satisfactory conclusion.

Medical Complaints/Adverse Events and Serious Adverse Events: DEX PS DDS

An AE is defined as any untoward medical occurrence in a subject or clinical investigation subject administered a pharmaceutical product and which does not necessarily have a causal relationship with this treatment. An AE can therefore be any unfavorable and unintended sign (including an abnormal laboratory finding), symptom, or disease temporally associated with the use of a medicinal (investigational) product, whether or not the event is considered causally related to the use of the product.

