4.2 Reporting Adverse Events, Product Complaints, and Intercurrent Illnesses

In the event of an SAE, whether associated with study drug or not, the investigator will notify Clinical Pharmacovigilance within 24 hours of the site being made aware of the SAE by entering the SAE data into the electronic data capture (EDC) system. Serious adverse events that occur prior to the site having access to the RAVE® system, or if RAVE is not operable, should be documented on the SAE non-CRF forms and emailed (preferred route) or faxed to Clinical Pharmacovigilance within 24 hours of the site being made aware of the SAE.

Email: [contact]
FAX to: [contact] Backup: [contact]

For safety concerns, contact the Ophthalmology Safety Team at:

Ophthalmology Safety Team
[name]
[name]
Toll Free: [contact]
Email: [contact]

For any subject safety concerns, please contact the physician listed below:

Primary Therapeutic Area Medical Director

EMERGENCY MEDICAL CONTACT:

[REDACTED] MD

AbbVie Inc.

[name]
[name]

Contact Information:

Mobile: [REDACTED]

Email: [REDACTED]

In emergency situations involving study subjects when the primary Therapeutic Area Medical Director is not available by phone, please contact the 24-hour AbbVie Medical Escalation Hotline where your call will be re-directed to a designated backup AbbVie Therapeutic Area Medical Director:

[REDACTED]
[contact]

The sponsor will be responsible for Suspected Unexpected Serious Adverse Reactions (SUSAR) reporting.

In the event of a product complaint occurring, the following procedure needs to be followed:

- Take pictures of the product immediately after the complaint occurs, focusing on the area with a complaint or defect if possible
- Do not discard the product
- Quarantine the product in question in appropriate container (such as a SHARPS container)
- Complete the Product Complaint eCRF within 24 hours of the event
- Hold sample at the site location until disposition or further instructions are provided by Sponsor's Product Complaint Team for possible product return.

For any questions, the site may email the Sponsor's Product Complaint Team at
[contact].

COVID-19 Pandemic-Related Acceptable Protocol Modifications

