11.0 Other Analyses

Not applicable.

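### Product complaints without an adverse event are collected but have no planned reporting, so applicator defects found before injection and failed deliveries may go unreported

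*Protocol*

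**What the plan says.** Protocol 2.1 explains the short follow-up by saying that "the duration of the proposed study is designed to capture investigator experience and any complaints associated with the DEX PS DDS Implant administration" with the updated applicator. The primary objective (Protocol 3.1, SAP 2.1) concerns the device: that it delivers the implant to the vitreous cavity and is fit to be marketed.

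Protocol 6.1 defines product complaints broadly. The examples include "missing components/product, device damage or not working properly, or packaging issues". Collection does not depend on harm: "Product complaints concerning the investigational product and/or device must be reported to AbbVie within 24 hours of the study site's knowledge of the event". Operations Manual 4.2 (Protocol Appendix F) repeats the duty: "Complete the Product Complaint eCRF within 24 hours of the event". Complaints are to be followed to a satisfactory end.

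Reporting is treated differently. On this, 6.1 says: "Product complaints associated with adverse events will be reported in the study summary. All other complaints will be monitored on an ongoing basis".

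The SAP does not mention product complaints, and its section "11.0 Other Analyses" is marked not applicable.

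**The concern.** In a drug-safety study it can be reasonable to report only complaints tied to an AE. Here the implant is unchanged, the study is stated not to be designed to assess the drug's efficacy or safety, and the question is whether the device works. A damaged needle tip noticed before use, or an actuator that releases nothing, bears directly on that question even if the patient is unharmed. Under 6.1 such an event is sure to be reported as a complaint only if an AE goes with it.

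The stake is the completeness of the device evidence. For either applicator, omitting complaints can only lower its count, so the updated applicator can only look better in its own right. The comparison between arms could move either way, because the same rule applies to the comparator.

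**Working it through.** **1. Number of applicators.** Protocol 7.8 and SAP 2.4 give minimums of 30 and 15 eyes and dropout of about 15%. Using n/(1 − d):

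- updated: 30/0.85 = 35.3, rounded up to 36
- currently approved: 15/0.85 = 17.6, rounded up to 18
- total: 36 + 18 = 54, the plan's own figure.

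The point changes no figure in the plan. It concerns what is reported on these 36 (at least 30) updated applicators.

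**2. Where each kind of failure would surface.** Four provisions matter:

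- The form asks whether the applicator dispensed the implant in the vitreous cavity and worked as it should, and is completed after administration (Operations Manual 3.13).
- Protocol 7.5 promises a summary of the form, within a section whose analysis is run on the Safety Analysis Set.
- That set holds only subjects who received the implant (Protocol 7.2, SAP 4.0).
- Complaint reporting follows the rule in Protocol 6.1.

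| Event, nobody harmed | Recorded as a complaint | On the Day 1 form | In the Safety Analysis Set | Complaint reporting promised |
|---|---|---|---|---|
| Malfunction during injection, implant delivered | Yes | Should be | Yes | No |
| Applicator delivers nothing, subject receives no implant | Yes | Possibly | No | No |
| Broken seal or damaged needle found before injection (Operations Manual 3.12, steps 6 and 12) | Yes | Not assured | Only if another unit is used | No |
| Complaint on unassigned product | Yes, on the back-up paper form | No | No subject | No |

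The first row has a second route through the form. In the other rows the non-AE complaint may be the only reportable record.

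**3. Size.** The documents give no malfunction or complaint rate, so what follows rests on assumed values.

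- One unreported complaint lowers the updated-arm rate by 1/36 = 2.8 percentage points, or 1/30 = 3.3 at the minimum sample.
- Chance of at least one failure, 1 − (1 − p)^n, for assumed p of 2%, 5% and 10%: with n = 30, 45%, 79% and 96%; with n = 36, 52%, 84% and 98%.
- Illustration with invented counts: 3 complaints on 36 updated applicators, one of them with an AE. All complaints: 3/36 = 8.3% (exact Clopper-Pearson 95% CI 1.8% to 22.5%). AE-linked only: 1/36 = 2.8% (0.1% to 14.5%).

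At this sample size one or two events visibly change the description of the device.

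**The case against.** The strongest reply is that the complaint log is not the study's main instrument for device failure. Applicator performance in both arms is a named additional endpoint (Protocol 3.4). The investigator records it on Day 1 whatever the AE status, the protocol says the form will be summarized, and indirect ophthalmoscopy after injection looks for the implant. Protocol 2.1 promises to capture complaints, and capture is complete: database entry within 24 hours, photographs, quarantine of the product, and follow-up. Nor does 6.1 forbid reporting the remaining complaints.

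Most of this stands. A reader might infer that applicator failures without harm are left out of the study altogether. The documents do not support that: all are collected, and those during injection should also be on the form. A reader might also take 2.8% against 8.3% as the error to expect. That is not supported either. The counts are invented, and no section defines a complaint rate or presents AE-linked complaints as the malfunction rate.

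The reply does not cover units rejected before injection or deliveries that fail outright. The form comes after administration, and the analysis set requires receipt of the implant. SAP 5.0 would show a subject as randomized but not treated, but it names no category for device failure. The SAP also plans no analysis of the form, although Protocol 7.1 leaves full analysis detail to the SAP. That is a separate gap; filling it would help with the first row of the table but not reliably with the others.

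The reply is also right that packaging and labelling complaints should not be mixed into a device-failure percentage. The fix keeps them apart.

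**Conclusion.** The point holds as a reporting gap, not a gap in data collection. Protocol 6.1 commits to reporting only AE-linked product complaints in the study summary, and the SAP adds nothing. Defects found before injection and applicators that delivered no implant may therefore be recorded only as non-AE complaints and never reported. The direction is certain for each applicator's own count: downward. The size is unknown, at 2.8 to 3.3 percentage points for each unreported complaint in the updated arm.

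This rests on two assumptions. First, the form has no field for failed or replaced units; its item list is not in the documents, so this cannot be checked. Second, the form is summarized on the Safety Analysis Set, as its place in Protocol 7.5 implies. If either is wrong, the gap is smaller. It should still be closed, because the omitted events bear on the primary objective and the data are already being collected.

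**What to change.** - **Protocol 6.1:** replace the two reporting sentences with a statement that all product complaints, with or without an AE, will be reported in the study summary by applicator.
- **SAP 11.0:** add a table of device-function complaints by type and arm, giving the number and percentage of applicators with at least one. The denominator should be applicators opened or attempted, not subjects who received the implant. Exact confidence intervals are optional in this descriptive study.
- **SAP 11.0:** add a listing of all other complaints, including packaging, labelling and unassigned product, which do not fit that denominator.

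The cost is one protocol sentence, one table and one listing. No new visits, subjects or assessments are needed. Complaints made on the back-up paper form must be brought into the listing, and the count of units opened should be checked against the kit numbers in the IRT system. The other downside is a complaint count that may be less favourable.

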7 STATISTICAL METHODS & DETERMINATION OF SAMPLE SIZE

7.1 Statistical and Analytical Plans

The statistical methods provided in this protocol will be focused on safety analyses. Complete and specific details of the statistical analysis will be described in the statistical analysis plan (SAP).

7.2 Definition for Analysis Populations

All subjects who have received DEX PS DDS Implant will contribute to the Safety Analysis Set (SAF). The SAF will be used for all safety analyses.

7.3 Handling Potential Intercurrent Events for the Primary and Key Secondary Endpoints

Not applicable for this study.

7.4 Statistical Analyses for Efficacy

This study is not designed to assess efficacy of the study drug. The DEX PS DDS Implant is an FDA-approved drug, and its efficacy is already well established.

Therefore, the efficacy analyses for this study are not applicable.

7.5 Statistical Analyses for Safety

The safety analysis will be performed using the SAF. General safety parameters will include AEs (including pregnancies that meet SAE criteria per Section 6.1) and vital signs. Ocular safety parameters will include BCVA, IOP measurement, biomicroscopy, ophthalmoscopy. The treatment administration assessment form will be collected to evaluate investigator experience with and performance of the updated and the currently-approved DEX PS DDS Applicators.

Adverse events will be coded using the Medical Dictionary for Regulatory Activities (MedDRA). The number and percentage of subjects reporting AEs will be tabulated based on primary system organ class and preferred terms. Summary tables will be generated for all AEs regardless of causality as well as treatment-related AEs. Descriptive statistics for vital signs will be presented. Ocular safety parameters will be summarized. The treatment administration assessment form will also be summarized.

7.6 Interim Analysis

Not applicable for this study.

7.7 Overall Type I Error Control

Not applicable for this study.

7.8 Sample Size Determination

The sample size is determined empirically based on discussions with FDA to evaluate a minimum of 30 eyes using the updated applicator and a minimum of 15 eyes using the currently approved applicator. Assuming a drop out rate of about 15% and the need to achieve 30 and 15 subjects to use the updated applicator and currently-approved applicator, respectively, the total enrollment would require approximately 54 subjects.

8 ETHICS

8.1 Institutional Review Board (IRB)

The protocol, informed consent form(s) (ICF[s]), recruitment materials, and all subject materials will be submitted to the IRB for review and approval. Approval of both the protocol and the ICF(s) must be obtained before any subject is enrolled. Any amendment to the protocol will require review and approval by the IRB before the changes are implemented to the study. In addition, all changes to the consent form(s) will be IRB approved.

8.2 Ethical Conduct of the Study

The study will be conducted in accordance with the protocol, Operations Manual, International Council for Harmonisation of Technical Requirements for Pharmaceuticals for Human Use (ICH) guidelines, applicable regulations, and guidelines governing clinical study conduct and the ethical principles that have their origin in the Declaration of Helsinki. Responsibilities of the investigator are specified in [Appendix B](#).

8.3 Subject Confidentiality

To protect subjects' confidentiality, all subjects and their associated samples will be assigned numerical study identifiers or "codes." No identifiable information will be provided to AbbVie.

9 SOURCE DOCUMENTS AND CASE REPORT FORM COMPLETION

The investigator is responsible for ensuring the accuracy, completeness, legibility, and timeliness of the data reported. All source documents should be attributable, legible, contemporaneous, original, accurate, and complete to ensure accurate interpretation of data. Clinical site monitoring is conducted to ensure that the rights and well-being of human subjects are protected, that the reported trial data are accurate, complete, and verifiable, and that the conduct of the trial is in compliance with the currently approved protocol, ICH Good Clinical Practice (GCP), and applicable local regulatory requirement(s). During the COVID-19 pandemic, remote data review/verification may be employed if allowed by the local regulatory authority, IRB, and the study site.

10 DATA QUALITY ASSURANCE

AbbVie will ensure that the clinical trial is conducted with a quality management system that will define quality tolerance limits in order to ensure human subject protection and reliability of study results. Data will be generated, documented, and reported in compliance with the protocol, ICH GCP, and applicable regulatory requirements.

11 COMPLETION OF THE STUDY

The end-of-study is defined as the date of end of study participation by the last subject in the study.

A subject is considered to have completed the study if he/she has completed all study visits including Day 7.

APPENDIX A. STUDY-SPECIFIC ABBREVIATIONS AND TERMS

Abbreviation	Definition
AE	Adverse event
BCVA	Best-corrected visual acuity
BRVO	Branch retinal vein occlusion
COVID-19	Coronavirus Disease – 2019
CRF	Case report form
CRO	Clinical research organization
CRVO	Central retinal vein occlusion
DEX PS DDS	Dexamethasone Posterior Segment Drug Delivery System
DME	Diabetic macular edema
eCRF	Electronic case report form
EDC	Electronic data capture
FDA	Food and Drug Administration
GCP	Good Clinical Practice
ICF	Informed consent form
ICH	International Council for Harmonisation of Technical Requirements for Pharmaceuticals for Human Use
IOP	Intraocular pressure
IRB	Institutional review board
IRT	Interactive response technology
MedDRA	Medical Dictionary for Regulatory Activities
NSAIDs	Nonsteroidal anti-inflammatory drugs
OU	Both eyes
PD	Premature discontinuation
PSC	Posterior subcapsular
RSI	Reference safety information
RVO	Retinal vein occlusion
SAE	Serious adverse event
SAF	Safety analysis set
SAP	Statistical analysis plan
SARS-CoV-2	Severe acute respiratory syndrome coronavirus 2
SE	Study eye

SUSAR

Suspected Unexpected Serious Adverse Reactions

APPENDIX D. ACTIVITY SCHEDULE

The following table shows the required activities across the study. The individual activities are described in detail in the Operations Manual. Allowed modifications due to COVID-19 are detailed in the Operations Manual.

Study Activities Table

Activity	Screening/ Baseline	Treatment administration	Day 2	Day 7/PD
	Day 3 to Day 1	Day 1	Day 2 + 1d	Day 7 ± 2d
❑ INTERVIEWS & QUESTIONNAIRES				
Informed consent	✓			
Eligibility criteria	✓			
Medical/surgical history (including demographics and ophthalmic history)	✓			
AE assessment	✓	✓	✓	✓
Prior/concomitant therapy (medications and procedures)	✓	✓	✓	✓
Treatment administration assessment form (completed by investigator)		✓		
LOCAL LABS & EXAMS				
Vital signs (blood pressure, pulse rate; at rest ≥ 5 minutes)	✓	✓	✓	✓
Urine pregnancy test (for female subjects of childbearing potential)	✓			
BCVA (Snellen equivalent)	OU		OU	OU
IOP measurement (prior to pupil dilation)	OU		OU	OU
Biomicroscopy exam (slit lamp)	OU		OU	OU
Ophthalmoscopy (indirect)	OU	SE	OU	OU
Rx TREATMENT				
Dispense study drug		✓		
Rx ADMINISTRATION				
Treatment administration (DEX PS DDS Implant 0.7 mg)		SE		

AE = adverse event; BCVA = best-corrected visual acuity; DEX PS DDS = Dexamethasone Posterior Segment Drug Delivery System; IOP = intraocular pressure; OU = both eyes; PD = premature discontinuation; SE = study eye

APPENDIX E. PROTOCOL SUMMARY OF CHANGES

Previous Protocol Versions

Protocol	Date
Version 1.0	20 April 2021
Version 2.0	24 June 2021

The purpose of Version 3.0 is to update from Version 2.0 the following sections below:

- Minor editorial changes were made throughout the protocol for clarity and consistency.
- On the Title page, the sponsor/emergency medical contact and the number of planned sites were updated.

Rationale: Updated due to personnel changes and revised number of planned sites.

- In Section 1, Section 2.1, Section 3.4, Section 7.5, and Appendix D, treatment administration questionnaire was revised to treatment administration assessment form.

Rationale: Revised to be consist with the terminology used on the eCRF.

- In Section 5.1 (eligibility criteria 7), added that diagnosis of macular edema due to RVO or DME is in the study eye.

Rationale: Revised for clarity and accuracy.

- In Section 5.8, text indicating that subjects could rescreen under their initial screening number was removed.

Rationale: Subjects are not to be rescreened using their initial screening number.

- In Section 5.10, location of criteria for subject withdrawal and adverse event reporting was provided.

Rationale: Updated to align with currently approved protocol template.

- In Section 6.1, details about product complaint reporting were added.

Rationale: Added to provide additional information on product complaint reporting.

- In Section 6.1, removed text indicating that AEs meeting SAE criteria can be reported to CRO.

Rationale: AEs meeting SAE criteria are to be reported to AbbVie clinical pharmacovigilance.

- In Section 8.2, removed text about conduct of the study in the event of a significant disaster/crisis.

Rationale: Removed to align with the currently approved protocol template.

- In Section 11, the end-of-study definition was revised from last subject's last visit to end of study participation by the last subject.

Rationale: Revised for clarity and to align with the currently approved protocol template.

- In [Appendix C](#), list of protocol signatories was updated
Rationale: *Updated due to personnel changes*
- [Appendix F](#) – the Operations Manual was updated as follows
 - In Section 1, the sponsor/emergency medical contact was updated, email address for SAE reporting was updated, and Product Complaints contact information was added.
Rationale: *Updated due to personnel changes and to align with additional product complaint reporting procedure details added to the protocol.*
 - In Section 2, guidance on timing administration of DEX PS DDS around the SARS-CoV-2 vaccine was added.
Rationale: *To align with guidance in the protocol.*
 - In Sections 2.1, 3.12, 3.13, and 6.4, treatment administration questionnaire was revised to treatment administration assessment form.
Rationale: *Revised to be consist with the terminology used on the eCRF.*
 - In Section 2.1, timing of administering the treatment administration assessment form was clarified.
Rationale: *Timing of administration was clarified for consistency.*
 - In Section 3.7, removed text indicating that the sponsor will provide the pregnancy test kits to sites.
Rationale: *The sponsor will not be providing the pregnancy test kits.*
 - In Section 3.8, distance from chart was converted from centimeters to inches.
Rationale: *Revised to be consistent with the use of feet for the Snellen equivalent.*
 - In Section 3.12 (step 12 under Treatment Procedure), instructions to inspect the needle tip were added.
Rationale: *To align with applicator instructions.*
 - In Section 4.1, text was added to clarify collection of AEs.
Rationale: *Clarification added to align with currently approved Operations Manual.*
 - In Section 4.2, removed the use of paper SAE CRFs, except as a backup, when reporting SAEs to clinical pharmacovigilance; email address for SAE reporting was updated.
Rationale: *To discontinue the use of paper SAE CRF forms except for use as a backup and to update contact information.*
 - In Section 4.2, added details about product complaints.
Rationale: *Product complaints will be collected.*
 - In Section 6.2, additional instructions about storage and disposition of study drug were added.
Rationale: *To provide additional detail and align with the currently approved Operations Manual.*

- In Section 7.2, subheading for the lens assessment was created.

Rationale: *To separate out the lens assessment and ophthalmoscopy (indirect).*

